7.7. Concomitant Therapy

All concomitant medication, whether prescription or over the counter, used at baseline and/or during the course of the study, must be recorded on the Concomitant Medication electronic case report form (eCRF). Patients will be instructed to consult the investigator or other appropriate study personnel at the site before taking any new medications or supplements during the study. For AD therapies permitted as part of rescue therapy, see Section 7.7.4.

7.7.1. Permitted Medications and Procedures

Treatment with concomitant AD therapies during the study is permitted only as described below.

- Daily use of emollients is required as background treatment. Moisturizers with additives containing pharmacological agents with antipruritic or antiseptic properties are not permitted. If daily applications are missed, it will not be considered a protocol violation
 - Patients should not apply emollients on the day of their study visit prior to the procedures to allow adequate assessment of skin dryness
- Background TCS therapy with moderate-potency and/or low-potency TCS (e.g., triamcinolone 0.1% cream and/or hydrocortisone 2.5% ointment) are to be used on active lesions, as described in Section 7.7.2
- Topical calcineurin inhibitors (e.g., tacrolimus and pimecrolimus), or topical PDE-4 inhibitor (i.e., crisaborole, where approved) are permitted in place of TCS on areas where application of TCS is considered inappropriate by the investigator; use should be limited to problem areas (e.g., face, neck, skin folds, genital areas, etc.) as described in Section 7.7.2

In addition, the following therapies are permitted during the study:

- For those patients on stable dosing of prescription sleep medications at entry, downward dose adjustments or discontinuation of treatment may occur during the study
- Nonsedating antihistamines including, but not limited to, acrivastine, bilastine, cetirizine, desloratadin, fexofenadine, levocetirizine, loratadine, mizolastine, and rupatadine are allowed for treatment of allergic conditions other than AD. Use of antihistamines for treatment of itch is not allowed during the study
- Single intra-articular or soft tissue (bursa, tendons, and ligaments) corticosteroid injection is allowed during the 16-week double-blind, placebo-controlled period
- Intranasal or inhaled steroid use is allowed
- Topical anesthetics and topical and systemic anti-infective medications are allowed
- Nonlive vaccinations are allowed; however, vaccination while receiving baricitinib may reduce efficacy of the vaccine
- ophthalmic drugs containing antihistamines, corticosteroids or other immunosuppressants are allowed

Any changes of these concomitant medications must be recorded in the Concomitant Therapy of Special Interest eCRF.

Treatment with concomitant therapies for other medical conditions such as diabetes and hypertension is permitted during the study.

7.7.2. Use of Topical Corticosteroids

A washout period of 14 days is required for all TCS prior to randomization at Visit 2.

At baseline (Week 0, Visit 2), patients will receive triamcinolone 0.1% cream (or equivalent-potency TCS) and hydrocortisone 2.5% ointment (or equivalent-potency TCS). See “Choice of Background Topical Corticosteroid” below. Triamcinolone 0.1% cream (moderate-potency TCS) should be applied at least once daily to affected areas until lesions are under control (clear or almost clear). Patients should then switch to hydrocortisone 2.5% ointment (low-potency TCS) and treat previously affected areas once-daily for 7 days and then stop. Hydrocortisone 2.5% ointment (low-potency TCS) may also be used to replace triamcinolone 0.1% cream (moderate-potency TCS) on areas of thin skin (face, neck, folds, and genital areas) and areas with skin atrophy.

If lesions reappear during the course of the study, the patients should resume the once-daily applications of triamcinolone 0.1% cream (moderate-potency TCS) or hydrocortisone 2.5% ointment (low-potency TCS) as described above.

Patients whose lesions persist or worsen despite the use of emollients and low- and/or moderate-potency TCS and/or patients who require daily applications on large surfaces may be considered for topical rescue with high- or ultra-high-potency TCS (Section 7.7.4 for details).

On the days of study visits, topical therapy including TCS should not be applied before the patient has undergone all study procedures and clinical evaluations in order to allow adequate assessment of skin dryness. Inability to follow this guidance for use of TCS will not be considered a protocol violation.

Choice of Background Topical Corticosteroid

Where possible, triamcinolone cream 0.1% and/or hydrocortisone 2.5% ointment will be supplied by the sponsor for use as background TCS. In the event of these specific TCS being unavailable, an alternate, equivalent-potency TCS may be provided by the sponsor (see below). Topical corticosteroid use, when supplied by the sponsor, should be recorded via weight of returned tubes as indicated in the Schedule of Activities (Section 2). In the event that the sponsor is unable to supply TCS, commercially available triamcinolone 0.1% cream and/or hydrocortisone 2.5% ointment may be supplied by the sites.

- Where providing triamcinolone 0.1% cream and/or hydrocortisone 2.5% ointment is not possible, an equivalent-potency TCS cream and/or ointment that is in line with local practices can be supplied by the sites. Refer to [Appendix 8](#) for guidance on potency equivalence.

- Where possible, TCS use when supplied by the site should also be recorded via weight of returned tubes, as indicated in the Schedule of Activities (Section 2); however, where this is not practical, this information does not need to be recorded, and will not be considered a protocol violation.
- If the TCS supplied by the sponsor is not considered suitable for an individual patient, an equivalent-potency TCS cream and/or ointment that is in line with local practices can be supplied by the sites. Refer to [Appendix 8](#) for guidance on potency equivalence.

Choice of High- and Ultra-High-Potency Topical Corticosteroids for Rescue

The use and choice of specific high- or ultra-high-potency TCS for rescue is at the discretion of the investigator and it will not be provided by the sponsor. The weights of returned tubes of the high- and ultra-high-potency TCS are not required.

Other Topical Treatments

Investigators may also select to use TCNIs and/or crisaborole in countries where approved, in place of TCS. If TCNIs or crisaborole are prescribed, use should be limited to problem areas (e.g., face, neck, skin folds, genital areas, etc.).

Use of all topical treatments for AD must be recorded in the CRF.

7.7.3. Prohibited Medications and Procedures

Prohibited Medications and Procedures Not Requiring Interruption of Investigational Product

The following therapies will not be allowed during the course of the study and, if taken by or administered to the patient, the prohibited therapy must be discontinued.

- High potency TCS (defined as any TCS with higher than moderate strength as defined in [Appendix 8](#)) except when given as rescue therapy as described in Section 7.7.4.
- topical antihistamines or sedating, systemic antihistamines including, but not limited to, alimemazine, chlorphenamine, clemastine, cyproheptadine, diphenhydramine, hydroxyzine, ketotifen, and promethazine
- Prescription allergen immunotherapy
- phototherapy including psoralen and ultraviolet A (PUVA), ultraviolet B, tanning booth and excimer laser
- bleach baths

Prohibited Medications Requiring Temporary Interruption of Investigational Product

The following therapies will not be allowed during the course of the study and, if taken by or administered to the patient, temporary interruption of investigational product is required.

- live vaccines (including Bacillus Calmette-Guérin [BCG] or herpes zoster), (see Exclusion Criterion [28])

- For BCG vaccination, investigational product should be temporarily interrupted for 12 weeks.
- For live herpes zoster vaccination, investigational product should be temporarily interrupted for 4 weeks.
- probenecid: if a patient is inadvertently started on probenecid, investigational product should be temporarily interrupted, and can be resumed after patient has discontinued probenecid. If a patient is not able to discontinue probenecid, then investigational product should be permanently discontinued

Prohibited Medications Requiring Permanent Discontinuation of Investigational Product

- systemic corticosteroids
- any systemic therapy, investigational or commercial (approved or off label use), used for the treatment of AD or symptoms of AD (except for antihistamines, as specified above)
- other JAK inhibitors (e.g., tofacitinib and ruxolitinib)
- systemic immunosuppressive/immunomodulatory substances, including, but not limited to, cyclosporine, methotrexate, mycophenolate mofetil, interferon γ , azathioprine, or biologic agents

Note: In the event that these prohibited medications were inadvertently used, agreement and documentation to continue investigational product must be sought from sponsor.

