Study I4V-MC-JAIY (JAIY) is a Phase 3, multicenter, randomized, double-blind, placebo-controlled, parallel-group, outpatient study evaluating the efficacy and safety of baricitinib 4-mg once daily (QD) plus topical corticosteroids (TCS) and 2-mg QD plus TCS, as compared to placebo plus TCS in adult patients with moderate to severe AD. The study population will include patients aged 18 years or older who have moderate to severe AD and a history of inadequate response to existing topical therapies.

The study duration will be up to 25 weeks over 3 study periods:

- Period 1: Screening Period lasting from 8 to 35 days prior to Week 0 (baseline, Visit 2).
- Period 2: Double-Blinded Treatment Period, lasting from Week 0 (baseline, Visit 2) through Week 16 (Visit 8) inclusive:
 - At completion of the double-blind treatment period, eligible patients will be provided the option to participate in the long-term extension study I4V-MC-JAHN (JAHN). Those not eligible or who chose not to participate will proceed to the post-treatment follow-up period.
- Period 3: Post-Treatment Follow-Up Period, spanning the period from the last treatment visit at Week 16 (Visit 8) or Early Termination Visit (ETV) to approximately 4 weeks following the last dose of investigational product.

Treatment Arms and Duration

Patients will be randomized at Week 0 to 1 of 3 treatment groups: placebo once daily (QD), baricitinib 2-mg QD, or baricitinib 4-mg QD. Use of TCS as a background therapy is allowed during the study. The study duration will be up to 25 weeks (Screening Period: up to 5 weeks prior to randomization; Double-Blinded Treatment Period: 16 weeks; Follow-up Period: approximately 4 weeks after the last dose of investigational product).

Number of Patients

This study will include approximately 300 patients with AD who will be randomized in a 1:1:1 ratio to receive placebo QD, baricitinib 2-mg QD or baricitinib 4-mg QD (100 patients in each treatment group).

Statistical Analysis

Unless otherwise specified, the efficacy and health outcome analyses will be conducted on the intent-to-treat population and safety analyses will be conducted on those patients who receive at least 1 dose of investigational product.

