If topical rescue therapy as described above fails to sufficiently control AD symptoms, then oral systemic medications may be used as rescue (e.g., corticosteroids, cyclosporine, and methotrexate); however, investigational product will be required to be permanently discontinued for the remainder of the 16-week study duration. If these medications are needed for other medical conditions (e.g., asthma flare), they will still be treated as rescue medications. These patients are still eligible to enter the long-term extension study (JAHN), if they complete the schedule of study visits through Visit 8 (Week 16) and are also able to complete a minimum 4-week washout from oral systemic rescue medications (which can occur during the screening period for Study JAHN).

Investigators should make every attempt to conduct efficacy and safety assessments immediately before administering any rescue treatment. An unscheduled visit can be used for this purpose if necessary.

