10.1. Sample Size Determination

Study JAIY will aim to enroll approximately 300 patients ≥ 18 years of age. The proposed sample size will ensure an 89% power to detect an absolute difference of 20% between the baricitinib 4-mg and placebo treatment groups and the baricitinib 2-mg and placebo treatment groups, each using a 2-sided alpha of 0.025 and a Fisher exact test, assuming a 10% placebo response rate for the primary endpoint. The assumptions are based on what was observed in the Phase 2 study (JAHG). The proposed end point of IGA 0 or 1 represents patients whose AD is clear or almost clear from a baseline of moderate or severe disease. The anticipated effect size represents 3 times more patients achieving this benefit compared to placebo, which, in discussion with therapeutic experts, is of a magnitude that is considered clinically relevant.

Sample size and power estimates were obtained from nQuery[®] Advisor 7.0.

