### 6.4. Handling of Dropouts or Missing Data

Intercurrent events (ICH E9 R1) are events which occur after the treatment initiation and make it impossible to measure a variable or influence how it would be interpreted.

Depending on the estimand being addressed, different methods will be used to handle missing data as a result of intercurrent events. Intercurrent events can occur through the following:

- application of one of the censoring rules (including after permanent study drug discontinuation or after rescue therapy)
- discontinuation

- missing an intermediate visit prior to discontinuation or rescue
- lost to follow-up.

Non-censor intercurrent events are events that are not due to the application of any censoring rule, i.e., the last 3 items in the list above.

Note that as efficacy and health outcome data can accrue after a patient permanently discontinues study drug or begins rescue therapy, specific general censoring rules to the data will be applied to all efficacy and health outcome observations subsequent to these events depending on the estimand being addressed. These specific censoring rules are described below.

The *primary censoring rule* will censor efficacy and health outcome data after permanent study drug discontinuation or after rescue therapy. This censoring rule will be applied to all continuous and categorical efficacy and health outcome endpoints. This censoring rule is equivalent to using all the data up to rescue.

A *secondary censoring rule* will only censor efficacy and health outcome data after permanent study drug discontinuation. This sensitivity analysis will include all observed values up to study drug discontinuation. The secondary censoring rule will be applied to primary and key secondary efficacy and health outcome endpoints as sensitivity analyses.

Table JAIY.6.1 describes the planned imputation methods for efficacy and health outcome endpoints with associated censoring rules. Sections 6.4.1 through 6.4.5 summarize the methodology of each imputation rule.

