## 6.10. Rescue Therapy

Rescue therapy with additional topical and systemic therapies is available starting after 2 weeks of treatment (Visit 4), for patients who are experiencing worsening and unacceptable symptoms of AD despite treatment with IP and moderate-potency TCS. Patients whose lesions persist or worsen despite the use of emollients and background TCS therapy (e.g., triamcinolone 0.1% cream and/or hydrocortisone 2.5% ointment) and/or patients who require prolonged applications

of triamcinolone 0.1% cream (moderate-potency TCS) on large surfaces may be considered for rescue to high- or ultra-high-potency TCS. If topical rescue therapy as described above fails to sufficiently control AD symptoms, then oral systemic medications may be used as rescue (e.g., corticosteroids, cyclosporine, methotrexate); however, investigational product will be required to be permanently discontinued for the remainder of the 16-week study duration. If these medications are needed for other medical conditions (e.g., asthma flare), they will still be treated as rescue medications.

The initial rescue therapy will be the first non-missing record before the last dose date from the CRF page *Concomitant Therapy: Rescue Therapy*.

A summary of the initial rescue therapy and the reason for requiring initial rescue will be produced, as well as a summary of the proportion of patients initially rescued at each study visit. A summary of all rescue medications will be provided.

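### Potent topical steroid used outside the rescue provisions meets neither trigger of the primary censoring rule, so a later IGA 0/1 can count as response

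*Protocol*

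**What the plan says.** **Effect of rescue.** Protocol 5.4 and 10.3.1 make a rescued patient a nonresponder from that point. SAP 6.4 implements this through a primary censoring rule that "will censor efficacy and health outcome data after permanent study drug discontinuation or after rescue therapy". SAP 6.4.1 and 6.12.1 apply it to IGA 0/1 with nonresponder imputation. Neither names prohibited medication as a trigger.

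**How rescue is found.** SAP 6.10: "The initial rescue therapy will be the first non-missing record before the last dose date from the CRF page" for rescue therapy. Protocol 7.7 and 7.7.1 describe two other medication pages (Concomitant Medication and Concomitant Therapy of Special Interest). Protocol 7.7.2 requires all topical AD treatment to be entered in the CRF, without saying on which page.

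**High- and ultra-high-potency TCS.** Protocol 7.7.3 prohibits them "except when given as rescue therapy as described in Section 7.7.4". They sit in the list of therapies that must be stopped without interrupting study drug. Protocol 7.7.4 opens rescue only after two weeks of treatment (Visit 4) and keeps patients rescued with these products on study drug.

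**Systemic drugs.** Protocol 7.7.3 lists systemic corticosteroids, cyclosporine, methotrexate and others as requiring permanent stopping of study drug, then adds: "In the event that these prohibited medications were inadvertently used, agreement and documentation to continue investigational product must be sought from sponsor". Protocol 7.7.4 requires permanent stopping after oral systemic rescue and says of those drugs: "If these medications are needed for other medical conditions (e.g., asthma flare), they will still be treated as rescue medications". SAP 6.10 repeats that sentence.

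**Phototherapy.** It is prohibited without interruption of study drug in 7.7.3 and is not named as rescue in 7.7.4 or SAP 6.10.

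**Elsewhere.** SAP 6.17 gives receipt of excluded therapy as a possible reason for exclusion from the per-protocol set.

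**The concern.** The primary estimand assumes that response is lost once a patient needs rescue. That works only if the treatment that defines rescue is recognised wherever it is used. For potent TCS, study drug continues whether the use is rescue or prohibited, so the discontinuation trigger cannot pick up what the rescue trigger misses. Two patients with the same exposure and the same Week 16 IGA can then be classified differently because of timing or the page the site chose. The credited response may come from the potent steroid, which is what the composite strategy is meant to exclude. The affected endpoints are IGA 0/1, the other responder endpoints under the same rule and, through censoring of scores, the continuous key secondary endpoints.

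**Working it through.** **1. The passages side by side**

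| Exposure | Entered as rescue | Not entered as rescue |
|---|---|---|
| High- or ultra-high-potency TCS | Study drug continues; rescue trigger met; nonresponder | Study drug continues; neither trigger met; observed IGA stands |
| Listed systemic drugs, default rule | Study drug stopped; nonresponder | Study drug stopped; nonresponder |
| Listed systemic drugs, study drug continued under the 7.7.3 Note | Rescue trigger met; nonresponder | Neither trigger met if the CRF page decides; nonresponder if SAP 6.10's any-reason sentence is applied by drug (oral drugs only) |
| Phototherapy | Not named as rescue | Study drug continues; neither trigger met |

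The first row is the main gap. The third is narrow. The fourth is an event without a rule. That the observed IGA stands is an inference from the two listed triggers; no sentence says so.

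**2. The plan's own power figure.** Protocol 10.1: "The proposed sample size will ensure an 89% power to detect an absolute difference of 20" percentage points, "each using a 2-sided alpha of 0.025 and a Fisher exact test, assuming a 10% placebo response rate for the primary endpoint", with "100 patients in each treatment group". Enumerating both binomials (n = 100, 0.10 and 0.30) and summing the probability of outcomes that favour baricitinib with two-sided Fisher p ≤ 0.025 gives 0.891. The stated 89% is reproduced.

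**3. Possible shift.** The documents give no frequency, so these inputs are assumptions. Shift in an arm = share with uncensored use × share of those users reaching IGA 0/1.

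- Low: 0.02 × 0.30 = 0.6 points. High: 0.06 × 0.50 = 3.0 points.
- Use of 6% on placebo and 2% on active: placebo rises by 0.06 × 0.30 = 1.8 to 0.06 × 0.50 = 3.0 points; active by 0.02 × 0.30 = 0.6 to 0.02 × 0.50 = 1.0 points.
- The difference narrows by 1.8 − 0.6 = 1.2 to 3.0 − 1.0 = 2.0 points, from 20 to between 18.8 and 18.0.

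**4. Illustrative effect on power** (same exact method, alpha 0.025)

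| Points added to placebo | Points added to baricitinib | Power |
|---|---|---|
| 0 | 0 | 0.891 |
| 1 | 0 | 0.842 |
| 2 | 0 | 0.782 |
| 3 | 0 | 0.714 |
| 3 | 1 | 0.764 |
| 2 | 2 | 0.861 |
| 0 | 2 | 0.939 |

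**5. How many patients decide the result.** With 30/100 responders on baricitinib, Fisher p is 0.0007 at 10/100 on placebo, 0.017 at 15/100 and 0.028 at 16/100. At the planned rates six placebo patients would have to change status to lose significance at 0.025. With 10/100 on placebo the smallest significant baricitinib count is 23/100, and with 12/100 it is 26/100, so near the boundary one or two patients suffice. The primary test is a Firth logistic regression; Fisher is used here because the sample size calculation uses it.

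**The case against.** The strongest reply is that most of the ground is covered.

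- **Systemic drugs.** Both sections stop study drug by default, and SAP 6.10 already treats the oral drugs as rescue whatever the reason. Continuing under the Note needs the sponsor's agreement, so it is not a site's choice of page. This stands. A reader might infer that any systemic steroid logged as a concomitant medication leaves the response intact; the documents do not support that beyond the Note.
- **Contradictory labels.** A reader might infer that 7.7.3 and 7.7.4 classify potent TCS inconsistently. They do not: 7.7.3 excepts rescue and refers to 7.7.4. What is missing is an analysis rule for use outside the exception. Nor is phototherapy classified twice.
- **The CRF page.** The page sentence in SAP 6.10 introduces rescue summaries, and the censoring rule in 6.4 cites no page. True, but it is the only operational definition of rescue in the SAP.
- **ITT.** Protocol 10.2 keeps patients who did not follow the protocol. That fixes who is analysed, not how a response after an intercurrent event is counted.
- **Existing sensitivity analyses.** The secondary censoring rule ignores rescue, so for patients who stay on drug its result does not depend on the label. The per-protocol set may drop users of excluded therapy. Both help interpretation; neither changes the primary result.
- **Protocol 8.2.** A patient who requires another effective agent not allowed as rescue leaves the study before starting it. That does not settle use that has already happened.
- **Size.** The 2-6% and 30-50% are assumptions, and 50% exceeds the planned active rate of 30% (10% + 20 points). This stands.

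**Conclusion.** The gap is real but narrow. Non-rescue use of high- or ultra-high-potency TCS has no rule in the ITT primary analysis, and following the plan can credit a response that the same product, entered as rescue, would remove. For systemic drugs the issue is limited to the 7.7.3 Note against 7.7.4, and those passages must be reconciled. Phototherapy is an unaddressed intercurrent event.

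The frequency is unknown. Under the stated assumptions an arm moves by 0.6-3.0 points. A reader might infer that this favours baricitinib. The documents do not show that: if use is mainly on placebo, the bias runs against baricitinib and the cost is power; it would favour baricitinib only if such use and response were commoner there. The figures do not show that the sample size is wrong. The case for change is that it is cheap and brings the analysis into line with the SAP's own composite estimand.

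**What to change.** In SAP 6.4 and 6.10, define the rescue intercurrent event by medication and start date, taken from every concomitant-medication CRF page and settled under blinded review before database lock. It should cover post-baseline high- or ultra-high-potency TCS and the systemic drugs that 6.10 already calls rescue, whichever page was used and whether or not study drug continued. The same blinded review should decide and record how phototherapy is handled. Keep the page-based definition as a sensitivity analysis, which also shows how many patients change status.

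Separately, the Note in Protocol 7.7.3 and the discontinuation text in 7.7.4 must be reconciled so that one passage governs each exposure. Which clinical rule applies is for the sponsor.

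The cost is SAP wording and a small amount of blinded medication review. Response rates may fall slightly, and a single stray application would count as nonresponse, as a single rescue application already does; the sensitivity analysis shows whether that matters.
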